We will select anonymised patients from the CALIBER cohort [15], which links four sources of electronic health data in England: the Clinical Practice Research Datalink (CPRD) with primary healthcare records, the Hospital Episode Statistics (HES) with hospital discharge information, and the Office for National Statistics (ONS) mortality and social deprivation data.

A patient will be included if he or she: a) was registered between January 1, 1998, and September 2015; b) aged 30 years or older at study entry; c) had no record of

previous diagnosis of cardiovascular disease; d) had been followed up for at least one year before the study entry; e) had at least one uric acid measurement.

Exposure

The main exposure will be the baseline serum uric acid (SUA) level measured within one year of the study entry as recorded in primary care. If a patient had more than one measurement, the mean of the values will be taken. We will perform sensitivity analyses to use the SUA level recorded closest to the study entry.

Since gout is an important complication of hyperuricaemia and is associated with CVDs, we will also classify the patient state at baseline as with gout or with no gout, regardless of SUA levels, based on the diagnosis within one year of the study entry. Participants who developed new-onset gout during follow-up will be analysed according to their baseline status of no gout.

Covariates

The following baseline covariates will be considered:

- a) Sociodemographic: sex, age and index of multiple deprivation;
- b) Cardiovascular risk factors: body mass index, systolic blood pressure, high-density lipoprotein (HDL) cholesterol, low-density lipoprotein (LDL) cholesterol, triglyceride, and estimated glomerular filtration rate, smoking status, alcohol consumption;
- c) Medication use: any prescription in the year before index date of blood pressure lowering drugs (including diuretics, beta blockers, ACEIs, ARBs), statins, non-steroidal anti-inflammatory drugs (NSAIDs), aspirin, immunosuppressant drug, and in women only, oestrogen oral contraceptives and hormone replacement therapy;
- d) Comorbidities (defined by Read codes, a coded thesaurus of clinical terms used in the UK, in primary care data and by ICD-10 codes in hospital care data): Cancer, diabetes, asthma or atopy, COPD, connective tissue disease, inflammatory bowel diseases.

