For continuous variables (BMI, systolic blood pressure, and cholesterol), we will use the most recent value in the year before the study entry. For alcohol consumption, we will use the most recent record in the five years before entry to classify participants' drinking behaviour into five categories: non-drinkers (Read codes as "teetotaller" or "non-drinker"), former drinkers (Read codes as "stopped drinking alcohol" or "ex-drinker"), occasional drinkers (Read codes as "drinks rarely" or "drinks occasionally"), current moderate drinkers (Read codes as "alcohol intake within recommended sensible limits" or "light drinker"), and heavy drinkers (Read codes as "alcohol intake above recommended sensible drinking limits" or "hazardous alcohol use").

We will impute missing covariate values using multiple imputation, as implemented in the “mice” algorithm in the statistical package R. We will extract the following values of the continuous variables to use as auxiliary variables for multiple imputation: the first measurement after the time window and the most recent measurement before the time window, along with the timing of these measurements relative to the study entry. We will check whether the imputations are plausible by comparing plots of the distribution of recorded and imputed values of all variables.

Follow up

The observation period for all participants will begin on the date when all the study inclusion criteria are fulfilled. Participants will be followed up until the occurrence of an initial presentation of cardiovascular disease, death, or de-registration from the practice, whichever occurred first.

Endpoints

Endpoints will be the initial presentation of cardiovascular disease as any of the following 13 CVDs diagnosed in primary care (defined by Read codes), secondary care (defined by ICD-10 codes), or at death.(defined by ICD-10 codes): Stable angina, unstable angina, myocardial infarction, unheralded coronary heart disease death, heart failure, cardiac arrest/sudden cardiac death, transient ischaemic attack, ischaemic stroke, subarachnoid haemorrhage, intracerebral haemorrhage, peripheral arterial disease, abdominal aortic aneurysm, atrial fibrillation, and a composite total cardiovascular disease (all 13 cardiovascular diseases combined). An example is given by the definition of atrial fibrillation [16]

Statistical analysis

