We will analyse the SUA level as a categorical variable in order to avoid presuming a particular shape for the association with CVDs. Since the normal range for SUA and the diagnosis cut-off for hyperuricemia diagnosis varies [17-19], we will use the following cut-offs:

- 1) 3 mg/dL (180 umol/L, the lower limit of target SUA level for long-term management recommended by the 2016 updated EULAR guideline [20]),
- 2) 4 mg/dL (240 umol/L),
- 3) 5 mg/dL (300 umol/L, the target SUA for severe cases or patients with tophi recommended by various guidelines [20-23]),
- 4) 6 mg/dL (360 umol/L, the general target SUA for long-term management recommended by various guidelines [20-23]),
- 5) 7 mg/dL (420 umol/L).

If the shape of the association between SUA and CVDs is found to be linear, we will then perform analyses with SUA level as a continuous variable.

Quantitative variables will be summarized in mean and standard deviation and qualitative variables in number and percentages. Between group differences of

parametric values will be compared using analysis of variance (ANOVA) and that of categorical variables using chi-square tests.

We will plot crude cumulative incidence curves for each specific cardiovascular endpoint for people with SUA levels between 240-300 umol vs. 360-420 umol/L, using age as the timescale, under a competing risks framework (i.e., participants could experience only one initial presentation).

We will use multivariable Cox regression to calculate cause-specific hazards for associations between categories of SUA levels and initial presentations of cardiovascular disease. We will plot Schoenfeld residuals to verify the proportional hazards assumption.

In the primary analysis, we will adjust for age (linear and quadratic), sex, index of multiple deprivation, diabetes, smoking status, BMI, systolic blood pressure, HDL cholesterol, LDL cholesterol, and prescription of statins or antihypertensive medication in the year before study entry. The baseline hazard function of each model will be stratified by general practice and sex, and we will use multiple imputation to account for missing covariate data.

Assuming independence in effects, heterogeneity in associations across CVD endpoints for the fourth vs. the first quintile will be assessed with tau-square statistic, which is the between-CVD endpoint variance, and I^2 that can be interpreted as the proportion of the total variation in estimates that is due to heterogeneity.

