We will conduct a series of sensitivity analyses:

- a) Covariate adjustment: We will conduct analyses adjusted for age and sex only, and analyses adjusted for age, sex, and cardiovascular risk factors. We will assess interactions with age and sex.
- b) Gout: We will categorise patients into with gout and with no gout, regardless of SUA.
- c) Imputed data: We will check whether the imputations are plausible by comparing plots of the distribution of recorded and imputed values of all variables.
- d) Data source: We will conduct analysis ignoring endpoints recorded only in primary care (CPRD).
- e) Endpoints: We will conduct analysis restricting endpoints to fatal endpoints.
- f) Time: We will conduct analysis restricting participants to individuals who entered the study after 2004 (when recording of covariates would be expected to be more complete after introduction of the Quality and Outcomes Framework to incentivise good performance in the care of specified diseases).

We will conduct all analyses using R 3.4.1.

Role of funding

The funders had no role in the study design, data collection, data analysis, data interpretation, or writing of the report.

References

[5] Kavousi, M. et al. Evaluation of newer risk markers for coronary heart disease risk classification a cohort study. *Ann Intern Med*. 156, 438–444 (2012).

[6] Storhaug, H. et al. Uric acid is a risk factor for ischemic stroke and all-cause mortality in the general population a gender specific analysis from The Tromso Study. *BMC Cardiovasc Disord*. 13, 115 (2013).

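### The Cox models give men and women the same age effect; freeing it by sex is a cheap safeguard, mainly for the planned SUA-by-sex interaction

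*Protocol*

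**What the plan says.** All of this is in the Protocol, Methods.

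- Statistical analysis, model: "We will use multivariable Cox regression to calculate cause-specific hazards for associations between categories of SUA levels".
- Statistical analysis, primary adjustment: "we will adjust for age (linear and quadratic), sex, index of multiple deprivation", followed by the other risk factors. No age-by-sex product is listed.
- Statistical analysis, strata: "The baseline hazard function of each model will be stratified by general practice and sex".
- Statistical analysis, crude cumulative incidence curves: "using age as the timescale, under a competing risks framework". No time scale is named for the Cox models.
- Sensitivity analysis (a): "We will conduct analyses adjusted for age and sex only, and analyses adjusted for age, sex, and cardiovascular risk factors", and then "We will assess interactions with age and sex". The natural reading of the second sentence is SUA-by-age and SUA-by-sex.
- Study population: participants are "aged 30 years or older at study entry", with no upper limit given.
- Follow up: "The observation period for all participants will begin on the date when all the study inclusion criteria are fulfilled". Together with age as a covariate, this points to time since entry as the Cox time scale.

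The Protocol gives no cardiovascular age gradient by sex, no SUA-age relation by sex and no expected number of events.

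**The concern.** For practice g and sex s the listed model is

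λ(t) = λ0,g,s(t) · exp(β1·age + β2·age² + Σ γk·[SUA category k] + other covariates).

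Sex enters through λ0,g,s(t), which lets the hazard over follow-up time differ between men and women. β1 and β2 have no sex index. The sex main effect in the covariate list drops out once sex is a stratum, so it adds nothing. A SUA-by-sex or SUA-by-age product does not free the age slope by sex either.

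With entry from age 30 upwards, age will be a dominant predictor. Where the true age slope differs by sex, the shared slope leaves an unfitted age trend of opposite sign in the two sexes. If SUA is correlated with age within a sex, the SUA terms pick up part of that trend. In the pooled hazard ratios the two sexes partly offset each other. In the SUA-by-sex contrast they need not, so that is the exposed result: an apparent sex difference in the SUA association could arise with no SUA effect at all.

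**Working it through.** There is no figure in the Protocol to reproduce. The check is a hand calculation of the mechanism, set against null simulations in which the true SUA hazard ratio is 1 in both sexes.

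**Inputs, all assumed.** Simulation A is a Cox model stratified by sex with 300,000 people and about 24,000-28,000 events. Age has mean 58 and SD 14. SUA has SD 70 µmol/L in women and 75 in men. Simulation B is a Poisson rate model with 600,000 people and about 85,000 events. Age has mean 60 and SD 13; SUA rises 1.5 µmol/L per year in women and is flat in men. Neither includes practice strata or the other covariates.

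**Hand formula.** If the age slopes differ by d per year and the shared slope falls near the middle, women keep an unfitted slope of +d/2 and men −d/2. Within a sex, age changes by ρ·SD(age)/SD(SUA) years per µmol/L. Per 60 µmol/L the spurious log hazard ratio is therefore ±(d/2)·60·ρ·SD(age)/SD(SUA).

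Example: d = 0.02, ρ = 0.25 in women and 0 in men. In women, 60 × 0.25 × 14/70 = 3.0 years, and 0.01 × 3.0 = 0.030. In men it is 0. The women/men ratio is exp(0.030) = 1.030.

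**Simulation A, women/men SUA ratio per 60 µmol/L.** The shift is the shared-age result divided by the sex-specific-age result on the same data. This removes simulation noise common to both fits.

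| d per year | ρ women | ρ men | Shared age | Age by sex | Shift | By hand |
|---|---|---|---|---|---|---|
| 0 | 0.25 | 0 | 1.001 | 1.002 | −0.1% | 0 |
| 0.01 | 0.25 | 0 | 1.015 | 1.001 | +1.4% | +1.5% |
| 0.02 | 0.25 | 0 | 1.030 | 1.001 | +2.9% | +3.0% |
| 0.02 | 0.15 | 0 | 1.024 | 1.007 | +1.7% | +1.8% |
| 0.02 | 0.35 | 0 | 1.042 | 1.004 | +3.8% | +4.3% |
| 0.02 | 0.20 | 0.20 | 1.028 | 0.985 | +4.4% | +4.7% |
| 0.02 | 0 | 0 | 1.006 | 1.007 | −0.1% | 0 |

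With no slope difference, or no SUA-age correlation, nothing material happens. Attained age as the time scale with sex strata agreed with the sex-specific fit to within about 0.001 in every row.

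**Pooled hazard ratios, simulation A.** For 360-420 versus 240-300 µmol/L the shifts are 1.007/0.997 = 1.010 (d = 0.01, ρ = 0.25 in women), 1.010/0.990 = 1.020 (d = 0.02, ρ = 0.25) and 1.019/0.992 = 1.027 (d = 0.02, ρ = 0.35). Above 420, with ρ = 0.20 in both sexes, it is 0.955/0.986 = 0.969. The size is thus about 1-3%, in either direction. That last shift is 0.032 on the log scale, or 1.4 standard errors (SE 0.023).

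**Top category against reference, simulation B.** With slopes of 0.07 in men and 0.09 in women, the women/men ratio at 420 or more was about 1.09-1.11 with shared age terms and 1.01-1.02 with sex-specific terms. A hand check takes SD 70 in women and the smallest gap from the middle of the reference category, 420 − 270 = 150 µmol/L. Age changes by 1.5 × 13²/70² = 0.0517 years per µmol/L, so 150 × 0.0517 = 7.8 years. For d = 0.02 this gives exp(0.01 × 7.8) = 1.08; for d = 0.01, exp(0.005 × 7.8) = 1.04. The range is therefore about 4-9%. Pooled hazard ratios ran from 0.96 (below 180) to 1.02, against 1.00-1.01 with sex-specific terms; 0.96/1.01 = 0.95 is the 5% in the sparse category.

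**Would the false interaction be significant?** The 5-df Wald statistic has a 5% critical value of 11.1.

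- d = 0.02, 85,000 events: 27.9 and 36.0 in two runs. Sex-specific age terms took the second to 5.8.
- d = 0.02, about 69,000 events: 18.3 and 15.0.
- Equal slopes of 0.09: 8.5 shared, 7.8 sex-specific.
- d = 0.01, about 72,000 events: 7.0, 7.8 and 11.4. Another run, at about 85,000 events, gave 11.7.
- d = 0.02, SUA trend halved to 0.75 per year, about 69,000 events: 10.4 and 5.7.
- d = 0.02, about 6,200 events: 10.6, 7.7, 12.1, 5.7 and 5.6.

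The last line agrees with simulation A. Its SE of 0.010 at about 26,000 events becomes 0.010 × √(26,000/6,200) = 0.020 at 6,200, so a log shift of 0.029 is only about 1.4 standard errors.

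**The case against.** Linear and quadratic age with sex strata is a conventional, coherent specification. Product terms between adjustment covariates, and the Cox time scale, are details often settled in a statistical analysis plan, and the same refinement could be asked of many covariate pairs. Every driver of the bias comes from outside the document, and the simulations omit practice strata, BMI, blood pressure, lipids, diabetes, smoking and drugs, so the bias under full adjustment is unknown. The most exposed result is one sentence within a sensitivity analysis, and hazard ratios in women are not a stated primary output. All of this stands, and it limits the point to an improvement.

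A reader might infer three stronger things that the document does not support.

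- That the curves on the age scale contradict the Cox models. They do not: the curves are crude and descriptive, the models are adjusted, and the two can use different time scales.
- That the primary SUA hazard ratios are seriously distorted. In the range examined they move by a few percent at most.
- That a false sex interaction will look significant. It did with very many events and both drivers strong; with a smaller slope difference, a weaker SUA trend or a single endpoint's events it mostly did not.

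What the objection does not remove is that the listed terms share the age slope across sexes, and that nothing else in the model or in the planned interaction check frees it.

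**Conclusion.** The mechanism is real and the remedy removes it, but its size is conditional. It needs both a sex difference in the age gradient and an SUA-age relation within sex, and it assumes time since entry as the Cox time scale, which the Protocol implies without stating. Under the assumed slope differences, the consequence for the pooled results is minor. For the SUA-by-sex interaction it is a bias of several percent, enough to mislead in the composite endpoint under the stronger assumptions but not dependably elsewhere. With few events significance weakens, though the bias itself remains. This is a cheap improvement of low-to-moderate priority.

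**What to change.** Either of these is sufficient:

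- Add sex-by-age and sex-by-age-squared terms to the Cox models, including the age-and-sex-only model in sensitivity analysis (a). At the least, include them in every model used to assess SUA-by-sex interaction.
- Use attained age as the Cox time scale, with delayed entry at the age of study entry, keep the sex strata, and state this in the text.

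In both cases, state which products the interaction analysis contains.

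The first option costs two parameters per model. The second costs none, although risk sets within practice-by-sex strata become smaller because people are compared at the same age. Either is a change of wording with no new data.

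### The primary Cox model omits alcohol consumption without a reason, and no planned model is the primary adjustment set plus alcohol

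*Protocol*

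**What the plan says.** Three parts of the Protocol's METHODS bear on this.

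- **Covariates, item b (cardiovascular risk factors)** ends with "triglyceride, and estimated glomerular filtration rate, smoking status, alcohol consumption". The whole covariate list is introduced by "The following baseline covariates will be considered".
- **Covariates, definitions** gives alcohol a detailed rule, with named Read code terms: the authors will "use the most recent record in the five years before entry to classify participants' drinking behaviour into five categories". The five are non-drinker, former, occasional, current moderate and heavy.
- **Statistical analysis, primary analysis** fixes the adjustment set. After age, sex and deprivation come "diabetes, smoking status, BMI, systolic blood pressure, HDL cholesterol, LDL cholesterol, and prescription of statins" or antihypertensive drugs in the year before entry. The baseline hazard is stratified by practice and sex. Alcohol does not appear, and no reason is given.

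Sensitivity analysis a) plans two alternative models: one with age and sex only, and one with age, sex and the cardiovascular risk factors. It does not name the variables in the second.

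**The concern.** A covariate is normally left out of an aetiological model because it may lie on the pathway from exposure to outcome, because it cannot be measured, or because it is irrelevant. The protocol offers none of these reasons for alcohol. It calls alcohol a cardiovascular risk factor and specifies how to extract it. It is also hard to see drinking as a consequence of SUA.

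If drinking raises SUA and also raises the hazard of some endpoints, the primary hazard ratios for the upper SUA bands absorb part of the alcohol association for those endpoints. The plan also compares associations across the 13 endpoints by tau-square and I². Confounding that acts on some endpoints and not others could therefore add to apparent heterogeneity as well as shift single estimates. Atrial fibrillation, heart failure and intracerebral haemorrhage are the endpoints where one would look first. The Introduction lists intracerebral haemorrhage among those not previously estimated.

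**Working it through.** **Step 1: compare the lists.** Item b of the covariates has eight variables.

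| Item b variable | In primary model? |
|---|---|
| BMI | yes |
| Systolic blood pressure | yes |
| HDL cholesterol | yes |
| LDL cholesterol | yes |
| Smoking status | yes |
| Triglyceride | no |
| eGFR | no |
| Alcohol consumption | no |

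Five enter and three do not. The omission is confirmed.

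**Step 2: does another planned model fill the gap?** Read the second model of sensitivity analysis a) as age, sex and all of item b. Relative to the primary set it adds three variables (alcohol, triglyceride, eGFR). It drops three others: deprivation (item a), medication (item c) and diabetes (item d). Six things change at once, so a shift in the hazard ratio could not be attributed to alcohol. The age-and-sex model contains no alcohol. No planned model equals the primary set plus alcohol.

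**Step 3: illustrative size.** The protocol states no effect size, event count or drinking prevalence, so there is no figure to reproduce, and every input here is an assumption. Treat heavy drinking against all other categories as one binary confounder. Let *p1* and *p0* be its share in the high and comparison SUA bands, and *R* its hazard ratio for the endpoint. The usual external-adjustment formula, approximate for hazard ratios, is

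bias factor = [1 + p1(R − 1)] / [1 + p0(R − 1)].

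With p1 = 15% and p0 = 5%:

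- R = 1.5: 1.075 / 1.025 = 1.049
- R = 2.0: 1.15 / 1.05 = 1.095

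Over a wider range of assumptions:

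| R | 15% v 8% | 15% v 5% | 20% v 10% | 25% v 8% | 30% v 5% |
|---|---|---|---|---|---|
| 0.8 | 0.986 | 0.980 | 0.980 | 0.965 | 0.949 |
| 1.0 | 1.000 | 1.000 | 1.000 | 1.000 | 1.000 |
| 1.2 | 1.014 | 1.020 | 1.020 | 1.033 | 1.050 |
| 1.5 | 1.034 | 1.049 | 1.048 | 1.082 | 1.122 |
| 2.0 | 1.065 | 1.095 | 1.091 | 1.157 | 1.238 |

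For a harmful effect (R from 1.2 to 2.0), the first three prevalence contrasts give about 1.01 to 1.10. The two sharper contrasts reach 1.16 and 1.24 at R = 2.0. Equal prevalence gives 1.00 whatever R is.

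**Step 4: how much could it explain?** For heavy drinking to turn a true hazard ratio of 1.0 into 1.2 at 15% v 5%, solve (1 + 0.15x) / (1 + 0.05x) = 1.2 with x = R − 1. This gives 0.09x = 0.2, so x = 2.22 and R is about 3.2.

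**The case against.** The case on the other side has real force.

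- *There is no contradiction.* The listed covariates are only to be considered, and several others (aspirin, NSAIDs, COPD, cancer) are also absent from the primary model. This stands: the primary set is a subset of a candidate list. The point is about an analysis choice left unexplained.
- *Alcohol is examined elsewhere.* On the natural reading, sensitivity analysis a) includes it. A reader might infer that the plan ignores alcohol altogether, and that would be wrong. What remains is that the check is not nested in the primary model.
- *The causal premise is not in the text.* The protocol labels alcohol a cardiovascular risk factor. It does not say that drinking is commoner at high SUA or which endpoints it affects. A reader might infer that the primary hazard ratios are inflated. The documents do not show this, and neither direction nor size is established.
- *Other covariates absorb part of it.* Sex, deprivation, smoking, BMI, blood pressure, HDL and antihypertensive use are conditioned on, whereas the formula uses unconditional shares and collapses five categories to two. This stands, and it is a reason to treat the table as illustrative only.
- *Adding alcohol has a price.* The auxiliary measurements planned for imputation are specified for continuous variables, so alcohol would be imputed without them. Sensitivity analysis f) also expects covariate recording to be more complete after 2004. This stands as a cost.
- *Why alcohol and not eGFR or triglyceride?* Their omission is also unexplained. They raise separate questions, and leaving them open does not weaken the point on alcohol.

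**Conclusion.** The point holds as a gap in the primary adjustment set. A baseline variable that the protocol calls a cardiovascular risk factor and defines in detail is left out of the headline model without a reason, and no planned model shows what adding it alone would do. The primary hazard ratios may therefore be confounded by drinking.

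Under assumed inputs the factor is about 1.01 to 1.10. It is larger with extreme prevalence differences, 1.00 if drinking is neutral or evenly spread across SUA bands, and below 1 where drinking is inversely related to the endpoint. This rests on alcohol being a common cause of SUA and of the endpoint in question, which is plausible but not stated in the protocol.

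It would go too far to say that a positive finding could not be told apart from alcohol. At the 15% v 5% contrast, heavy drinking would need a hazard ratio of about 3.2 to produce a hazard ratio of 1.2 by itself, and sensitivity analysis a) gives a partial check. A shift of a few per cent still matters if the true associations are close to 1, and the correction uses a variable already planned for extraction.

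**What to change.** 1. Add alcohol consumption to the primary Cox adjustment set in its five defined classes, as unordered categories, because former drinkers have no place on an intake scale.
2. Include the same variable in the multiple imputation model.
3. Keep the present adjustment set as a sensitivity model. It is then nested in the primary model, and the shift due to alcohol can be read off for each endpoint.
4. Name the variables in the second model of sensitivity analysis a), so that it is clear whether deprivation, diabetes and medication stay in.

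If the authors prefer to leave alcohol out of the primary model, they should give the reason and add one model that is the primary set plus alcohol.

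The cost is four more coefficients in each endpoint model and the imputation of a categorical variable that lacks the before-window and after-window measurements specified for continuous covariates. No new data definition is needed.

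### The primary model adjusts for blood-pressure drugs without separating diuretics, which can leave residual confounding in the SUA hazard ratios, most plausibly for heart failure

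*Protocol*

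**What the plan says.** **Primary model.** The Statistical analysis section of the protocol specifies "We will use multivariable Cox regression to calculate cause-specific hazards for associations between categories of SUA levels" and the initial presentations. It then lists the primary adjustment set, which ends with "LDL cholesterol, and prescription of statins or antihypertensive medication in the year before study entry". No drug class is named there.

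**Covariates, item c.** Medication use is defined as "any prescription in the year before index date of blood pressure lowering drugs (including diuretics, beta blockers, ACEIs, ARBs", followed by statins and other drugs. Diuretics are thus one of four named classes under a single heading.

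**Exposure.** The exposure is the "baseline serum uric acid (SUA) level measured within one year of the study entry as recorded in primary care". This period can overlap the look-back year for prescriptions.

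**Sensitivity analysis a.** "We will conduct analyses adjusted for age and sex only, and analyses adjusted for age, sex, and cardiovascular risk factors". The cardiovascular risk factors are item b of the Covariates section: body mass index, systolic blood pressure and lipids, then "triglyceride, and estimated glomerular filtration rate, smoking status, alcohol consumption". That item contains no drugs.

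**The concern.** The exposure is a substance cleared by the kidney, as the Introduction says. Diuretics affect that clearance; the other blood-pressure drugs need not do so in the same way. Diuretics may also be started for symptoms that come before a coded diagnosis of heart failure, which is one of the 13 endpoints. Diuretic use can therefore be related both to the SUA band and to the outcome.

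A pooled antihypertensive term compares treated patients with one another as if their drugs were interchangeable. If treated patients in the higher SUA bands include more diuretic users, and those users carry a different risk, part of that difference is credited to SUA. The bias may also differ between endpoints, and would then enter the planned tau-square and I² comparison of associations across endpoints.

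**Working it through.** The protocol states no event count, class prevalence or effect size on this point, so there is no figure to reproduce. The check has two parts.

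**1. Does any listed analysis isolate diuretics?**

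- Primary model: statins or antihypertensives. This can mean one combined indicator or two; neither separates diuretics.
- Sensitivity a: age and sex only, or with item b of the covariates. Item b has no drugs. The interactions named are with age and sex.
- Sensitivities b to f: gout, plausibility of imputations, data source, fatal endpoints, entry after 2004. None adjusts for, stratifies by or restricts on diuretic use.
- Estimated glomerular filtration rate is a listed covariate but is not in the primary set, so that model does not capture renal handling of urate by this route either.

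**2. How large could the residual bias be?**

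All inputs here are assumptions:

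- true SUA rate ratio 1.00;
- 30% of patients in the high-SUA group;
- any antihypertensive in 25% (low SUA) vs 45% (high SUA), or in 30% vs 60%;
- rate ratio 1.3 for treated with a non-diuretic class vs untreated;
- rate ratio R for diuretic vs other class;
- diuretic share among treated patients d_low and d_high.

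The pooled adjustment is represented by a Mantel-Haenszel rate ratio stratified on any antihypertensive (yes/no):

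w_s = n_low,s × n_high,s / (n_low,s + n_high,s)

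RR = Σ w_s × rate_high,s / Σ w_s × rate_low,s

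Relative rates are 1 in untreated patients and 1.3 × [1 + d × (R − 1)] in treated patients.

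*Worked case:* treated 30% vs 60%, diuretic share 30% vs 70%, R = 2.0.

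- Untreated: n_low = 0.7 × 0.7 = 0.49; n_high = 0.3 × 0.4 = 0.12; w = 0.0588/0.61 = 0.0964.
- Treated: n_low = 0.7 × 0.3 = 0.21; n_high = 0.3 × 0.6 = 0.18; w = 0.0378/0.39 = 0.0969. Rates are 1.3 × 1.3 = 1.69 (low) and 1.3 × 1.7 = 2.21 (high).
- RR = (0.0964 + 0.0969 × 2.21) / (0.0964 + 0.0969 × 1.69) = 0.3106/0.2602 = 1.19.

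Pooled-adjusted SUA rate ratio, true value 1.00 (each range covers the two assumed treated shares):

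| Diuretic share, low vs high SUA | R = 1.0 | R = 1.2 | R = 1.5 | R = 2.0 |
|---|---|---|---|---|
| 40% vs 40% | 1.00 | 1.00 | 1.00 | 1.00 |
| 40% vs 50% | 1.00 | 1.009–1.011 | 1.020–1.025 | 1.037–1.046 |
| 35% vs 60% | 1.00 | 1.021–1.027 | 1.051–1.064 | 1.096–1.118 |
| 30% vs 70% | 1.00 | 1.034–1.044 | 1.083–1.104 | 1.156–1.194 |

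In the rows with unequal shares and R from 1.2 to 2.0, the unadjusted ratio runs from 1.08 to 1.43. The pooled term therefore removes part of the confounding but not all of it. With a separate diuretic term the ratio returns to 1.00 by construction.

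*Direction:* in the worked case with R = 0.8, the treated rates are 1.3 × 0.94 = 1.222 (low) and 1.3 × 0.86 = 1.118 (high). RR = (0.0964 + 0.0969 × 1.118) / (0.0964 + 0.0969 × 1.222) = 0.2048/0.2148 = 0.95. The bias then runs towards an inverse association.

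**The case against.** **The design already limits the problem.** Patients with a prior cardiovascular diagnosis are excluded, which removes known heart failure. The primary model also adjusts for systolic blood pressure, body mass index and diabetes. This stands as mitigation. It does not cover prescribing before a diagnosis is coded, and it does not separate the classes.

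**The coding of the drug term could be settled in an SAP.** No SAP was available here, and the protocol does not say how the term is coded. But it writes out the primary adjustment set and the sensitivity analyses, and neither names diuretics. Pooling is the natural reading of what is stated.

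**Timing is not fixed for each patient.** A prescription in the look-back year may follow the SUA measurement, so diuretic use need not have influenced the measured value. This stands; it is a further reason to speak of possible bias.

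**Stronger readings that the document does not support:**

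- *That the hazard ratios are confounded as a matter of fact.* The document gives neither the class mix by SUA band nor the risk by class.
- *That the bias always produces a false positive association.* The R = 0.8 case contradicts this, and the other classes have indications of their own.
- *That the bias within treated patients is the bias in the reported hazard ratio.* With assumed diuretic shares of 60% vs 25%, the factor [1 + 0.60 × (R − 1)] / [1 + 0.25 × (R − 1)] is 1.12/1.05 = 1.07, 1.30/1.125 = 1.16 and 1.60/1.25 = 1.28 for R = 1.2, 1.5 and 2.0. These values hold only among antihypertensive users. The planned model estimates over treated and untreated patients together, and this mechanism adds nothing among the untreated.
- *That the protocol itself shows an ARB acting on SUA in the opposite direction.* Reference 8 concerns losartan and uric acid, but its title gives no direction.

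**Conclusion.** The point holds as one of possible residual confounding. The stated primary set does not separate diuretics from other blood-pressure drugs, and no listed sensitivity analysis makes good the gap. The pharmacological premise is general knowledge and not a statement of the protocol.

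Two conditions are needed for bias: a class mix that differs by SUA band, and a risk in diuretic users that differs from that in users of other classes, both beyond the covariates already adjusted for. If either fails, the bias is nil. The figures up to about 1.19 illustrate what the assumed inputs imply; they do not estimate the effect in this cohort. Heart failure is the most plausible endpoint to be affected. This is a cheap improvement to the model and does not invalidate the design.

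**What to change.** In the primary analysis paragraph of the Statistical analysis section, replace the joint statin and antihypertensive item with three separate baseline indicators for the year before study entry: statin, diuretic, and other antihypertensive. Add one sensitivity analysis that repeats the SUA models in patients with no diuretic prescription in that year. Splitting loop from thiazide diuretics is optional.

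The Covariates section already names diuretics among the prescription data, so no new data source is needed. The cost is a few extra model terms, and fewer events, hence wider intervals, in the restricted analysis.
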